8.1.1.4 Analysis Datasets

Population:

Enrolled: This will comprise all subjects who meet the eligibility criteria and are registered onto the study.

A Phase II, Single-arm Study of Combination Pembrolizumab and Olaparib in the Treatment of Patients with Advanced Cholangiocarcinoma

Version 2.1: 17Mar2023

Evaluable: This will comprise all subjects who receive at least one dose of olaparib and pembrolizumab trial drug and either undergo at least one post-baseline assessment or die before any evaluation. Non-evaluable patients will be replaced.

Intention-to-treat (ITT): This will comprise all subjects who meet the eligibility criteria and are registered onto the study irrespective of their compliance to the planned course of treatment. (See ITT principle below*)

Per Protocol Set (Valid Cases, Efficacy Sample, Evaluable Subjects Sample): This will comprise all subjects who complied with the protocol sufficiently to ensure that these data would be likely to exhibit the effects of treatment, according to the underlying scientific model. Compliance covers such considerations as exposure to treatment, availability of measurements and absence of major protocol violations. This population should be specifically defined in the protocol.

Safety: This will comprise all subjects who have received at least one dose of olaparib and one dose of pembrolizumab that contribute data to the safety analysis.

Treated: This will comprise all subjects who have been exposed to the planned course of treatment to any extent.

8.2 Statistical Analysis Plan

8.2.1 Analysis Plans for Primary Objective

The overall response rate will be estimated with its 95% exact confidence interval. Safety summaries will be presented by the severity of the adverse event and by relationship to study drug. Descriptive statistics (minimum, maximum, mean median, standard deviation for continuous variables; counts, percentages for categorical variables) will be used in summarizing of all laboratory and safety parameters (adverse events, serious adverse events, adverse events leading to discontinuation, deaths) for all treated subjects.

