8.1.1.3 Sample Size and Accrual

The primary objective of the study is to assess the ORR of patients with advanced cholangiocarcinoma receiving a combination of pembrolizumab and olaparib. It is hypothesized that the combination of olaparib and pembrolizumab will improve the overall response rate (ORR) from 17.5% (historical control) to 35% in patients with advanced cholangiocarcinoma. The sample size is based on the number of patients that are anticipated to complete the primary objective.

Simon's two-stage Optimum design will be used to test the null hypothesis of $P \leq 0.05$ versus the alternative hypothesis of $P \geq 0.25$. At the first stage, 13 patients will be treated with the combination of olaparib and pembrolizumab. The trial will be terminated if 2 or fewer patients respond. If there are more than 2 responses, the trial will go on to the second stage and 20 more patients will be enrolled to a total of 33 patients. If the total number responding among the 33 patients is ≤ 8 , the null hypothesis will not be rejected and the combination of olaparib plus pembrolizumab will not be investigated further. Using this statistical method, there is a 0.092 (9.2%) probability of erroneously concluding that this drug combination is effective when it actually is not (targeted value of 0.1). If the drug is actually effective, there is a 0.192 probability of concluding that it is not (targeted value of 0.2). The power of the design is 85% with a one-sided significance level of 0.05. If we assume a 10% patient dropout rate, then a total of 36 patients will be needed for the trial.

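### The planned 95% exact interval for ORR matches neither the level nor the two-stage structure of the decision rule, so 9 or 10 responses in 33 count as success while the interval contains 17.5%

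*Combined protocol and SAP*

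**What the plan says.** Section 8.2.1 gives the whole efficacy analysis of the primary endpoint in one sentence: "The overall response rate will be estimated with its 95% exact confidence interval". It names no exact method, gives no p-value, does not mention the interim stage, and does not say whether the interval bears on the decision. The rest of the section concerns safety summaries.

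The decision rule is in section 8.1.1.3. Stage 1: "At the first stage, 13 patients will be treated with the combination of olaparib and pembrolizumab", and "The trial will be terminated if 2 or fewer patients respond". Otherwise "the trial will go on to the second stage and 20 more patients will be enrolled to a total of 33 patients". At the end, "If the total number responding among the 33 patients is ≤ 8 , the null hypothesis will not be rejected", so 9 or more of 33 is a success. The section states error probabilities of 0.092 (target 0.1) and 0.192 (target 0.2).

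The same section is inconsistent about what is tested. Its hypothesis is that the combination will "improve the overall response rate (ORR) from 17.5% (historical control) to 35% in patients with advanced cholangiocarcinoma", but the null and alternative printed beside the Simon design are 5% and 25%. It also claims 85% power at a one-sided level of 0.05.

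**The concern.** A reader of the final report will have two primary results: a verdict from the boundary and an interval from 8.2.1. They are built to different standards. The rule tests at a one-sided level of about 0.09 and allows for the stage 1 stop. A two-sided 95% interval corresponds to a one-sided level of 0.025 and, if computed in the ordinary way, treats all 33 patients as one sample. For some totals the rule will reject the historical rate while the interval includes it. Because the plan does not say which governs, either reading could be argued once the data are known.

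**Working it through.** **Inputs.** From 8.1.1.3: n1 = 13, stop at 2 or fewer; n2 = 20, n = 33, success at 9 or more; rates 17.5% and 35%; stated errors 0.092 and 0.192. From 8.2.1: 95% exact interval. Assumptions: Clopper-Pearson method and denominator 33, since 8.2.1 specifies neither.

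**1. Reproduce the plan's error rates.** The probability of reaching stage 2 with at least s responses in total is

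S(s, p) = Σ (x = 3 to 13) P[Bin(13, p) = x] · P[Bin(20, p) ≥ s − x].

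- S(9, 0.175) = 0.0922, matching the stated 0.092.
- 1 − S(9, 0.35) = 1 − 0.8084 = 0.1916, matching the stated 0.192.
- The printed 5% and 25% give a type I error of 0.00002 and power of 0.391. They do not reproduce.
- The claim of 85% power at one-sided 0.05 does not reproduce either: the rule has 80.8% power at 9.2%.

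The operating null is therefore 17.5%.

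**2. Compare the intervals and p-values with the rule.** One-stage figures use Bin(33, p). Two-stage figures use stage-wise ordering, in which every trial that reaches stage 2 ranks above every trial stopped at stage 1. The two-stage p-value is S(s, 0.175), and the lower bound at one-sided level a solves S(s, p) = a.

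| Responses of 33 | One-stage 95% CI | Two-stage 95% CI | One-stage p vs 17.5% | Two-stage p vs 17.5% | One-stage 90% lower bound | Two-stage 90% lower bound |
|---|---|---|---|---|---|---|
| 9 | 13.3% to 45.5% | 13.7% to 48.1% | 0.109 | 0.092 | 17.2% | 17.8% |
| 10 | 15.6% to 48.7% | 15.9% to 50.1% | 0.051 | 0.045 | 19.8% | 20.1% |
| 11 | 18.0% to 51.8% | 18.1% to 52.5% | 0.021 | 0.020 | 22.4% | 22.6% |

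All three totals are successes. The ordinary 95% interval first excludes 17.5% at 11.

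**3. Separate the two causes.** Allowing for the stages while keeping 95% raises the lower limit only from 13.3% to 13.7% at 9 and from 15.6% to 15.9% at 10, so 17.5% stays inside. Changing the level to the target one-sided 0.10 while ignoring the stages resolves 10 (19.8%) but not 9 (17.2%, p = 0.109). Doing both resolves 9 as well (17.8%, p = 0.092). Level is the main cause; the stages matter at the boundary itself.

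**4. How often it happens.** At a true ORR of 35%, P(9 in total, stage 1 passed) + P(10 in total, stage 1 passed) = 0.0783 + 0.1103 ≈ 0.189. As a share of successes, 0.1887 / 0.8084 = 23%. At a true 17.5%, 0.0727 / 0.0922 = 79% of the false successes fall at 9 or 10.

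**5. Coverage of the ordinary interval** (on 13 patients if stopped, on 33 otherwise). It is 98.0% at a true 17.5%, 95.4% at 25% and 97.7% at 35%. The minimum is about 94.4%, near 36%.

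**6. Bias of the observed proportion.** Over all trials, including those stopped at stage 1, it is −2.6 points at a true 17.5% and −1.5 at 35%. Among trials that continue, x/33 is on average too high: +4.2 and +1.1 points. The UMVUE is unbiased over all trials, but among those that continue its bias is +10.6 and +2.8 points.

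**The case against.** The strongest reply is that nothing is invalid. The boundary is pre-specified, and no section makes success depend on the interval excluding 17.5%. The interval is an estimation summary with coverage near or above 95%, and an interval that contains 17.5% at 9/33 fairly shows that the evidence there is weak (p = 0.092). Against the printed null of 5% there is no conflict at all, since the lower limit at 9/33 is 13.3%.

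Much of this stands. It limits the point to interpretation and supports keeping a 95% interval. It does not remove the point, because the plan never says that the boundary governs or that the interval is descriptive, and the printed 5% null is incompatible with the stated error rates. The sentence claiming a one-sided level of 0.05 adds a third standard, which 9/33 would also miss.

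Three stronger readings are tempting but unsupported:

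- A reader might infer that ignoring the two stages produces the contradiction. The two-stage 95% intervals also contain 17.5% at 9 and 10.
- A reader might infer that x/33 understates the ORR once the trial continues. The negative biases average over stopped trials; given continuation the bias is upward.
- A reader might say that the SAP prescribes a single-stage method. It says only that the interval is exact, so the plan is silent on this.

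**Conclusion.** The concern holds as a mismatch between the reported interval and the decision rule, mainly in level and secondarily in sample space. It affects totals of 9 and 10, with probability 18.9% at a true ORR of 35% (23% of successes). It does not show an invalid test or material undercoverage.

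The conclusion rests on three assumptions: 17.5% is the operating null, the interval is Clopper-Pearson, and the denominator is 33. With all 36 planned enrolments as denominator, the lower limits at 9, 10 and 11 responses would be 12.1%, 14.2% and 16.3%, so the mismatch would extend to 11. The conflict in 8.1.1.3 between 5%/25% and 17.5%/35% is more basic and has to be reconciled first.

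**What to change.** In 8.1.1.3, reconcile the printed null and alternative, and the sentence on 85% power at one-sided 0.05, with the rule and its stated error rates.

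In 8.2.1, add that:

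- the efficacy decision rests on the 8.1.1.3 boundary;
- the exact two-stage p-value against 17.5% is reported, with a stage-wise-ordering lower bound at the test's target level (one-sided 90%). At 9/33 these are 0.092 and 17.8%, in agreement with the rule;
- a 95% interval, preferably stage-wise, is given and labelled descriptive, with its method and denominator named.

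The UMVUE (30.8% at 9/33, against an observed 27.3%) may be added as a supplement. It should not be the headline estimate, because its bias among trials that continue is larger than that of x/33.

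The cost is a few lines of text and standard code, with no change to enrolment or conduct. The downside is a less familiar interval reported beside the 95% one.

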8.2.2 Analysis Plans for Secondary Objectives

Progression free survival (PFS) and overall survival (OS) will be evaluated using the methods of Kaplan and Meier (1958). 95% confidence interval will be constructed for the estimated median PFS and OS. The exploratory overall response rate will be estimated with its 95% exact confidence interval.

8.2.3 Analysis Plans for Exploratory Objectives

The biomarkers which are of interest are programmed death ligand-1 (PD-L1) levels, immune score as determined by the density of CD3 and CD8 in the tumor interior and invasive margin(s) of the tumor, the clonality of the T-cell repertoire in the tumors, the expression of ERCC, and the mutation status of IDH1 or 2 in the same cholangiocarcinoma tissue. We will assess the biomarker levels at baseline, after four weeks of combination olaparib and pembrolizumab therapy, and at the time of cancer progression. The expression of ERCC and the mutation status of IDH1 or 2 in

A Phase II, Single-arm Study of Combination Pembrolizumab and Olaparib in the Treatment of Patients with Advanced Cholangiocarcinoma

Version 2.1: 17Mar2023

the same cholangiocarcinoma tissue will only be assessed at baseline. For different levels of biomarkers at baseline or change between different time points, we are interested in correlating them with patients' response, PFS, OS, and DOR

The density of CD8+ cells, CD3+ cells, and the expression of PD-1 and PD-L1 in the same cholangiocarcinoma tissue at baseline, after four weeks of combination olaparib and pembrolizumab therapy, at the time of cancer progression, and the changes between different time points will be summarized using descriptive statistics (N, Range, Median, Mean, STD). The paired t-test will be used to examine the changes in each biomarker level from the same tumor prior to any treatment at four weeks after the combination of olaparib and pembrolizumab, and at the time of cancer progression. These biomarkers levels and changes may be categorized into high or low levels based on the distribution of the data collected. The response of different biomarker levels (high vs. low) at baseline, at 4 weeks after combination treatment with olaparib and pembrolizumab, or at the time of cancer progression will be compared via Chi-Square test or Fisher's Exact test when appropriate. The relationship between these biomarker levels, their changes, and the DOR and PFS will be explored via Kaplan-Meier methodology and Log-rank test.

Similar analyses will be done for the Shannon Diversity Index (SDI) of T cell clonality in tumor samples.

The expression of ERCC (DRCC+/-), and the mutation status of IDH1 or 2 (mutant or non-mutant) in the same cholangiocarcinoma tissue at baseline will be summarized using descriptive statistics (N, frequency). The response of ERCC- or IDH1/2 wild type tumors at baseline will be compared with the response of ERCC+ or IDH1/2 mutant tumor using Chi-Square test or Fisher's exact test when appropriate. The relationship between these biomarker levels and the DOR and PFS will be explored via Kaplan-Meier methodology and Log-rank test.

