7.1.2.7 Tumor Tissue Collection and Correlative Studies Blood Sampling

7.1.2.7.1 Biospecimen studies and Procedures

We propose that olaparib will increase the response of pembrolizumab by inducing DNA damage, increasing tumor antigen number and producing durable immune response against cholangiocarcinoma. The cancer cells with low expression of the ERCC1 proteins or with IDH1/2 mutations will have more DNA damage upon olaparib treatment compared to that with normal expression of the ERCC1 protein, or without IDH1/2 mutations.

In this study, we will first test the effect of olaparib and pembrolizumab treatment on tumor infiltrating lymphocytes, the level of PD-1 and PD-L1 expression, and clonality of the T-cell repertoire differ between low ERCC1/IDH1/2 mutant and normal ERCC1/no IDH1/2 mutant. Then we will examine whether the change of tumor infiltrating lymphocytes, the level of PD-1 and PD-L1 expression correlates with clinical response in patients treated with pembrolizumab and olaparib combination therapy.

Immunohistochemical (IHC) staining: The level of PD-1 and PD-L1 expression in tumor biopsy will be measured by immunohistochemical (IHC) staining at Merck laboratories.

Immunohistochemical (IHC) staining, Digital image acquisition and analysis: The density of intratumoral total (CD3+) and cytotoxic (CD8+) T lymphocytes will be measured in the tumor interior (TI) and in the invasive margin (IM) of the three biopsied tumor samples. Immune cell densities will be obtained by immunohistochemistry and quantified using a biomarker imaging system in tandem with Image J processing software at Lombardi Comprehensive Cancer Center. Immune cell density in the TI and IM was converted to a binary score (0 as Low, 1 as High), with a cutoff threshold determined by the median density of CD3+ and CD8+ cells. We previously carried out a study on the association of intratumoral CD3 and CD8 cell density with recurrence free survival in patients with surgically resected Hepatocellular Carcinoma.

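### The continuous biomarkers are related to outcome only through high/low groups; a continuous-scale test would recover power at almost no cost

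*Combined protocol and SAP*

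**What the plan says.** Section 8.2.3 states an interest in correlating baseline marker levels, and changes between time points, with response, PFS, OS and DOR. The continuous markers are CD3 and CD8 density, PD-1, PD-L1 and the Shannon diversity index of T-cell clonality. On categorisation it says: "These biomarkers levels and changes may be categorized into high or low levels based on the distribution of the data collected".

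The tests follow from that. Response in high versus low groups "will be compared via Chi-Square test or Fisher's Exact test when appropriate". For time to event: "The relationship between these biomarker levels, their changes, and the DOR and PFS will be explored via Kaplan-Meier methodology and Log-rank test". The same approach is extended to the diversity index. No marker test is named for OS.

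Section 7.1.2.7.1 gives a specific rule for the T-cell densities only: a binary score "with a cutoff threshold determined by the median density of CD3+ and CD8+ cells".

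Two parts of the plan are not affected. Within-patient change keeps the continuous scale: "The paired t-test will be used to examine the changes in each biomarker level from the same tumor". ERCC and IDH1/2 are binary by nature; Section 8.2.3 describes "the mutation status of IDH1 or 2 (mutant or non-mutant) in the same cholangiocarcinoma tissue at baseline".

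**The concern.** A correlation aim for continuous measurements has been turned into comparisons of two groups. Cutting a continuous marker treats a patient just above the cut like one far above it, and discards the ordering within each half. The cost falls on a small trial in which patients are asked for up to three biopsies, and where a real association could easily be missed.

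The plan is also incomplete in two ways. Outside CD3 and CD8, no cut is fixed for PD-1, PD-L1, the diversity index or the change scores. And OS, a stated aim, has no marker analysis.

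**Working it through.** **Inputs from the plan.** Section 8.1.1.3 gives the number of patients: "20 more patients will be enrolled to a total of 33 patients". Enrolment is 36 to allow for dropout. The stated response rates are 17.5% (historical) and 35% (target). The plan gives no power, sample size or precision for the biomarker analyses, so every marker effect size below is an assumption.

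**Check of the design the inputs come from.** The rule is to continue with more than 2 responses in 13 and to succeed with more than 8 in 33. The success probability is the sum over x = 3 to 13 of P(X1 = x) × P(X2 ≥ 9 − x), with X1 ~ Bin(13, p) and X2 ~ Bin(20, p).
- p = 0.175: 0.0922, against the stated 0.092.
- p = 0.35: 0.8084, so the type II error is 0.1916, against the stated 0.192.

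The stated error rates therefore belong to 33 patients and 17.5% versus 35%, and 33 and 35% are used below.

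**Information kept by a split.** For a normal marker cut at quantile q, with c the normal quantile of q, the fraction kept is φ(c)² / [q(1 − q)]. At the median this is 2/π = 0.637.

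| Cut at percentile | Fraction kept | Equivalent patients out of 33 |
|---|---|---|
| 50th | 0.637 | 21.0 |
| 30th or 70th | 0.576 | 19.0 |
| 25th or 75th | 0.539 | 17.8 |
| 20th or 80th | 0.490 | 16.2 |

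Thirty-three is a favourable figure. The flow chart footnotes let later biopsies be waived, which reduces the number for change scores. If the trial stops at stage 1, a median split leaves 13 × 0.637 = 8.3 patient-equivalents.

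**Power for response.** Simulation of 6,000 trials per row: N = 33, response rate 35%, logistic relation to a standard normal marker, two-sided 5%, patient at the median scored low.

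| Odds ratio per SD (assumed) | Continuous score test | Wilcoxon | Median split, chi-square | Median split, Fisher |
|---|---|---|---|---|
| 1 (no association) | 5.1% | 4.6% | 5.1% | 2.9% |
| 2 | 39.7% | 36.9% | 28.5% | 22.1% |
| 2.5 | 60.6% | 56.9% | 44.1% | 35.8% |
| 3 | 73.9% | 70.0% | 55.2% | 47.4% |

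Against chi-square, the split costs 8 points (36.9 − 28.5) to 19 points (73.9 − 55.2). Fisher costs more, partly because its true size here is 2.9% rather than 5%. Simulation error is at most about √(0.25/6000) = 0.6 points.

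**Power for PFS.** With D events and a hazard ratio HR per SD, power is about Φ(√D × ln HR − 1.96) for the continuous marker. For a median split, D is replaced by 0.637 × D. With an assumed D = 30 and HR = 1.5:
- continuous: Φ(5.477 × 0.405 − 1.96) = Φ(0.26) = 60%
- median split: Φ(4.370 × 0.405 − 1.96) = Φ(−0.19) = 43%

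At HR = 1.75 the figures are 87% and 69%.

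**DOR.** Only responders count: 0.35 × 33 = 11.6, about 12, so a median split compares about 6 with 6.

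**The case against.** The strongest reply is that these analyses are exploratory and that the wording permits a split rather than requiring one. No sample size, decision rule or primary conclusion depends on them, and high/low splits are common at this stage. Continuous summaries and paired t-tests are also planned. All of this is true and sets the low priority. It does not remove the point: no continuous alternative is named, and the named outcome tests cannot be run without groups.

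Section 7.1.2.7.1 describes the median rule in the past tense, so it may be carried over from earlier work. It is still the only cut the documents give.

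Two stronger readings are tempting.

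- **Inflated false positives.** A reader might infer that a cut taken from the collected data will create spurious associations. Picking the best of 11 cuts between the 25th and 75th percentiles by their result would raise the false-positive rate to about 22%. But the plan refers to the distribution of the data in a sentence about marker levels and changes. That most naturally means the marker's own distribution, and such a cut does not inflate the error: the median split gave 5.1% with chi-square and 2.9% with Fisher. No passage describes a search on outcome. What remains is that most cuts are not fixed.
- **A collapse in power.** With 10 responders, 20 non-responders and a 1-SD shift, Fisher on a median split has about 20% power against about 66% for Wilcoxon. Most of that gap is the discreteness of Fisher's test: 8 of 10 versus 7 of 20 gives p = 0.0502, and the actual size is 0.5%. Chi-square, which the plan also allows, gives about 53% in the same setting. The expected counts there are 5, 5, 10 and 10, so the usual rule would select it. That contrast is not a fair measure of the cost of splitting.

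**Conclusion.** The point holds as a low-priority improvement to the exploratory analysis. For the continuous markers, the plan relates level and change to response, PFS and DOR only through grouped tests, and names no marker test for OS.

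The loss at a median split is about 36% of the information. That is roughly 8 to 19 percentage points of power for response against chi-square over the odds ratios examined, and about 18 points for PFS at the hazard ratios shown. These figures assume a normally distributed marker, a linear effect on the log-odds or log-hazard scale, 33 patients with tissue, a 35% response rate and, for PFS, 30 events. The margin varies with the exact number of responders and with how ties at the median are scored.

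The primary ORR result, the paired t-tests and the ERCC and IDH1/2 comparisons are unaffected. The documents do not support a claim that the plan inflates type I error.

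**What to change.** Amend Section 8.2.3 as follows.

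- **Response:** make the Wilcoxon rank-sum test on the continuous marker the main test, or exact or penalised logistic regression where an estimate with a confidence interval is wanted.
- **PFS and OS:** use Cox regression on the continuous value, reported as a hazard ratio per SD with its confidence interval. Log-transform positive-valued levels only. Change scores can be negative, so leave them untransformed or use log-ratios. This also supplies the missing OS analysis.
- **DOR:** describe it, or fit the same Cox model with a warning that about 12 responders are expected and the estimate will be unstable.
- **Grouping:** fix a median split in advance for all continuous markers and their changes, state which side the median patient falls on, and use it only for Kaplan-Meier display.
- **ERCC and IDH1/2:** keep as binary.

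The cost is SAP wording and slightly more analysis, with no new data. The Cox model adds a linearity assumption, which should be stated and checked as far as the numbers allow.

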3.2 Secondary Objective(s) & Hypothesis(es)

(1) Objective:

1. Assess the duration of response (DOR) of patient receiving pembrolizumab and olaparib, taking best overall response to progression.
2. Assess progression free survival (PFS) of patients receiving pembrolizumab and olaparib taking best overall response to progression or death from any cause, whichever occurs first.
3. Assess overall survival (OS) of patients receiving pembrolizumab and olaparib from baseline to date of death or last follow up.
4. Assess the safety and tolerability of combined pembrolizumab and olaparib therapy.

(2) Hypothesis:

We propose that a PFS of 24 weeks and an OS of 40 weeks is clinically meaningful in patients who receive the combination of pembrolizumab and olaparib following failure on frontline therapy (due to cancer progression or intolerance of treatment).

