4.5.2 Secondary Endpoints

The secondary study endpoints are the duration of response (DOR), progression free survival (PFS), and overall survival (OS) in patients receiving the combination therapy. All of these endpoints are part of the clinical response assessment.

Primary Endpoint Definition

1. The objective response rate (ORR) is the proportion of all subjects with confirmed PR or CR according to RECIST 1.1, from the start of treatment until disease progression/recurrence (taken as reference for progressive disease, the smallest measurements recorded since the start of treatment).

Secondary Endpoint Definition

1. PFS is defined as the duration from the date of registration until disease progression (as defined above; using RECIST 1.1) or death occurs. Subjects who have not progressed will be right-censored at the date of the last disease evaluation.
2. OS is defined as the time of registration until death as a result of any cause.
3. Overall response rate (ORR) is defined as the sum of complete response (CR) + confirmed partial response (PR) and will be determined using the immune-related response criteria (iRECIST).
4. Grade 3 and 4 toxicities as defined by the NCI Common Terminology Criteria for Adverse Events (NCI CTCAE) v4.

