8.1.1.2 Endpoints

1. Definition of Primary Endpoint

- a. Efficacy endpoint: overall response rate (ORR): defined as the proportion of subjects who achieve the best response (CR and PR) determined by RECIST1.1.

2. Definition of Secondary Endpoints

- a. PFS: defined as time from registration till the patient's disease progression or death from any cause whichever occurs first (those for whom event of progression or death not observed will be censored).
- b. OS: defined as time from registration till the patient's death from any cause (patient who are still alive at the end of the study will be censored).
- c. Overall response rate: defined as the proportion of subjects who achieve the best response (CR and PR) determined by irRC.
- d. To assess duration of response (DOR) of patients with advanced cholangiocarcinoma receiving a combination of pembrolizumab and olaparib.
- e. Safety endpoint: patients' toxicity profile, adverse event, serious adverse event, serious adverse even leading to discontinuation of the treatment, death. Safety and tolerability of the combination of olaparib and pembrolizumab is assessed by CTCAE v4.

A Phase II, Single-arm Study of Combination Pembrolizumab and Olaparib in the Treatment of Patients with Advanced Cholangiocarcinoma

Version 2.1: 17Mar2023

3 Definition of Exploratory Endpoints

- a. To correlate the baseline density of CD3 and CD8 in the tumor interior and invasive margin of the tumor, the expression of PD-L1, and the clonality of the T-cell repertoire with ORR, DOR, PFS, and OS.
- b. To correlate the difference between the baseline density of CD3 and CD8 in the tumor interior and invasive margin of the tumor, the expression of PD-L1, and the clonality of the T-cell repertoire and the same assessments after three weeks of treatment with ORR, DOR, PFS, and OS.
- c. To compare the density of CD3 and CD8 in the tumor interior and invasive margin of the tumor, the expression of PD-L1, and the clonality of the T-cell repertoire at three time points: at the time of disease progression, after three weeks of treatment, and at baseline.
- d. To correlate in the cholangiocarcinoma tissue the baseline expression of ERCC (DRCC+/-) or the baseline mutation status of IDH1 or 2 (mutant or non-mutant) with ORR, DOR, PFS, and OS.

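### Section 8.2.3 relates biomarker values taken at progression to response, PFS and DOR, although that sample exists only because the patient has progressed

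*Combined protocol and SAP*

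**What the plan says.** Section 8.2.3 measures the tumour markers at baseline, "after four weeks of combination olaparib and pembrolizumab therapy, and at the time of cancer progression". Levels and changes may be cut into high and low according to the data observed. Response by high or low level is to be tested on the pre-treatment sample and on the later ones, with Fisher's exact test as the alternative: "at 4 weeks after combination treatment with olaparib and pembrolizumab, or at the time of cancer progression will be compared via Chi-Square test". For time-to-event outcomes the section continues: "The relationship between these biomarker levels, their changes, and the DOR and PFS will be explored via Kaplan-Meier methodology and Log-rank test". The levels and changes meant are those just described, so the progression sample is included.

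The time origins lie before that sample. Section 8.1.1.2 gives "PFS: defined as time from registration till the patient's disease progression or death from any cause", and Section 4.5.2 also starts PFS at registration. For DOR, Section 3.2 has "Assess the duration of response (DOR) of patient receiving pembrolizumab and olaparib, taking best overall response to progression".

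The objectives ask for less. In Sections 3.3 and 8.1.1.2, tumour-marker correlations with outcome are listed for baseline values and for the on-treatment (three-week) assessment. Objective 3 and endpoint 3c use the progression sample only in a comparison across the three time points.

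No section specifies a landmark, a time-dependent covariate or a rule for patients without a later biopsy. Footnote 7 of the flow chart in Section 6.1 allows later biopsies to be waived.

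**The concern.** A patient has a progression sample only after progressing, and it is collected at about the moment that ends PFS and DOR. Grouping patients by that value explains an interval with something measured at its end. For response, the supposed predictor is measured after the outcome. Patients who have not progressed, including ongoing responders, have no value and leave the comparison, as do patients who die without a progression biopsy.

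The practical risk is confounding with elapsed time. If a marker moves steadily while patients are on treatment, those who progress late have had longer to drift, and the log-rank test reads this as a PFS difference. Section 4.5.3 hypothesises that treatment alters lymphocyte infiltration and PD-1/PD-L1 expression, so some movement is expected. A shift common to all patients that is complete early would not track elapsed time. Drift is therefore plausible, but the documents do not quantify it.

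**Working it through.** The plan states no error rate for these analyses, so there is no figure to reproduce.

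**1. Inputs from the documents.** Total sample 33 (Section 8.1.1.3: "20 more patients will be enrolled to a total of 33 patients"). Response rate under the alternative 35% (same section: "from 17.5% (historical control) to 35% in patients with advanced cholangiocarcinoma"). Median PFS 24 weeks as the hoped-for value (Section 3.2) and 3.0 months for second-line chemotherapy (Section 4.5), which is 3.0 × 52/12 = 13 weeks. First scan at week 6 (Section 7.1.2.6.2).

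**2. Inputs assumed.** Exponential PFS, a median split, no true effect of the marker, two-sided 0.05, and the strength of drift. None of these is in the documents.

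**3. Progression level against PFS, correlation scale.** 28 progressors (assumed), median PFS 24 weeks. Marker value = ρ × standardised time to progression + √(1 − ρ²) × independent normal noise, then median split and log-rank.

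| ρ | Rejection rate |
|---|---|
| 0 | about 6% |
| 0.2 | about 14% |
| 0.3 | about 23% |
| 0.5 | about 51% |

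**4. The same question, drift scale.** n = 33 and 3,000 simulated trials per cell. Further assumptions: hazard × 0.6 after week 6 in responders and × 1.2 in non-responders; censoring uniform over 52–156 weeks; within-patient noise 0.7 SD; every PFS event has a sample. Drift is in baseline SD per week. Cells show the 13-week / 24-week median.

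| Test | Drift 0 | Drift 0.02 | Drift 0.05 |
|---|---|---|---|
| Level at progression vs PFS | 0.062 / 0.071 | 0.282 / 0.388 | 0.790 / 0.925 |
| Change to progression vs PFS | 0.066 / 0.053 | 0.563 / 0.760 | 0.984 / 0.998 |
| Level at progression vs DOR | 0.071 / 0.066 | 0.150 / 0.167 | 0.398 / 0.482 |
| Level at progression vs response (Fisher) | 0.020 / 0.023 | 0.043 / 0.039 | 0.122 / 0.073 |

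The Monte Carlo standard error at 0.05 is √(0.05 × 0.95 / 3000) = 0.004. The DOR row rests on about 9–11 responders who progressed.

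**5. On-treatment sample.** In the same simulation, a week-4 level tested against PFS from registration among biopsied patients rejects 0.054–0.069 of the time in every scenario, identical to a week-4 landmark. Every biopsied patient, high or low, shares the same event-free time, and subtracting a constant does not change the log-rank ranking. If unbiopsied patients were counted as low, which the plan does not exclude, the rate would be 0.116–0.127 (13-week median) or 0.072–0.081 (24-week median).

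**6. Patients lost before the on-treatment biopsy.** With exponential PFS the proportion with an event by week w is 1 − 2^(−w/median).
- Week 3: 1 − 2^(−3/24) = 8.3% and 1 − 2^(−3/13) = 14.8%, or 2.7 to 4.9 of 33.
- Week 4: 1 − 2^(−4/24) = 10.9% and 1 − 2^(−4/13) = 19.2%, or 3.6 to 6.3 of 33.

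**The case against.** The strongest reply is that this is a drafting mismatch in an exploratory section. The log-rank sentence does not name the progression sample, an earlier sentence in 8.2.3 speaks of baseline levels or changes between time points, and the objectives confine outcome correlations to baseline and on-treatment data. The one explicit misuse, response by level at progression, shows little error inflation. The larger PFS figures depend on assumed drift. Without drift the test stays near nominal, and at a correlation of 0.2 about 86% of null trials would not reject.

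Much of this stands: the inflation is conditional and its true size unknown. It does not remove the point. The response comparison at progression is explicit, changes between time points include changes to progression, and nothing in 8.2.3 limits the log-rank sentence. Exploratory status excuses low power and multiplicity, but not a predictor that can be observed only at the event.

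Three stronger inferences are not supported:
- A reader might infer that the on-treatment sample carries the same bias because PFS starts at registration. That biopsy, at week 3 or week 4, precedes the first scan at week 6, and only biopsied patients have a level, so the test keeps its size (step 5). What remains is plotted curves that include guaranteed event-free time, unstated exclusion of early events and no missing-biopsy rule.
- A reader might infer that every drifting marker will look prognostic. The figures show a raised probability, not a certainty.
- A reader might infer that the results decide which biomarkers go forward. The documents say only that associations will be examined; no selection rule depends on them.

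**Conclusion.** The point holds for progression samples. Section 8.2.3 tests response explicitly, and PFS and DOR by its wording, against a value that exists only after progression. This is circular, drops ongoing responders and serves no listed objective. For PFS, the false-positive rate of a nominal 5% log-rank rises from about 6% with no drift to about 14%, 23% and 51% at correlations of 0.2, 0.3 and 0.5 with elapsed time. Those figures depend on the assumed correlations, 28 progressors and median split, with median PFS set at the plan's 24 weeks. For response the inflation is at most about 12% under the drifts tried, and the fault there is mainly temporal order and selection. For the on-treatment sample there is no error-rate problem among biopsied patients. The primary ORR decision is unaffected. The change is worth making because it costs little and removes an analysis that cannot be interpreted as prediction.

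**What to change.** In Section 8.2.3:

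1. State that progression samples are used only for description and for paired comparison with baseline and on-treatment samples, in line with objective 3 and endpoint 3c. Remove the comparison of response by level at progression, and exclude progression-time levels and changes to progression from the log-rank analyses.
2. Relate response, PFS, OS and DOR only to baseline levels and to the on-treatment level or its change from baseline.
3. For the on-treatment value, start the PFS and OS curves at the biopsy date among patients event-free then. This corrects the plotted time origin; it is not needed to protect the error rate.
4. State that patients without an on-treatment biopsy are not assigned to a high or low group, and report how many are excluded and why (early event, waived, other).
5. First reconcile the on-treatment biopsy timing: Section 7.1.2.7.2 places it in the third week and Section 8.2.3 after four weeks.

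The cost is SAP wording. No new data are needed and no listed objective is lost. Patients with an event before the on-treatment biopsy are absent from that analysis, but they have no on-treatment value under the current plan either.
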